CLINICAL STUDY PROTOCOL

Interventional Drug or Biologic

Examining the Effect of Varying Water Content of E-liquids on Sensory Experience

Protocol Number

2000031495

NCT05257109

Protocol Version

5-25-22

Version # 3

PRINCIPAL INVESTIGATOR:

Name: [name]

Department: Psychiatry

[contact]

Email Address: [contact]

IND Number:

IND Holder:

NCT Number: N/A

Study Phase (1, 2, 3, or 4-postmarketing):

Confidentiality Statement:

REVISION HISTORY:

Revision #	Version Date
3	5-25-22

Synopsis

Primary Objective

The primary objective of this study is to examine whether (a) sensory irritation and (b) appeal are decreased in e-liquids containing flavor aldehydes (i.e. vanilla, cherry, cinnamon) compared to e-liquids not containing flavor aldehydes (i.e. grape) when the water concentration is increased from the baseline water concentration to the following levels; 5% total water volume, 10% total water volume, 20% total water volume.

Secondary Objective (if applicable)

At each water concentration, we will examine if there are differences in perception of sensory irritation and appeal across the distinct aldehyde containing flavors.

Study Duration

2 years to complete study from HIC submission; we anticipate the subject enrollment period will be 8 months (approximately 1 week/participant). Enrollment began in August 2022, so anticipated subject enrollment will end in March 2023.

Study Design

Within subjects' human laboratory experiment

Number of Study Sites

1; Yale School of Medicine. Yale sites include Connecticut Mental Health Center (intake visits) and John B. Pierce Laboratory (lab sessions).

Study Population

Population is regular e-cigarette users who report use of both nicotine and flavors in their e-cigarettes. We are assessing response to alterations of water level in e-cigarettes among regular users as a potential regulatory tool, so current participants must have regular nicotine experience.

Number of Participants

30; pilot study

Primary Outcome Variables

- (1) Change in irritation at each water level as measured by the Generalized Labeled Magnitude Scale (gLMS)
- (2) Change in appeal at each water level as measured by the Labeled Hedonic Scale (LHS), Drug Effects Questionnaire (DEQ)

Secondary and Exploratory Outcome Variables (if applicable)

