E-liquid Administration/Participant Instructions/Pausing due to AEs: Participants will be administered e-liquid in an observed laboratory setting in which they are instructed to take two directed puffs of each e-liquid at each water concentration. Between 2-puff puff bouts, participants will be required to wait 10-minutes before engaging in next puff bout. Participants are not allowed to leave the site with product. There will no changes in nicotine concentration (only flavor administered) and all participants will sample all flavor/water concentration manipulations. The lab sessions will be conducted by trained research staff who are sensitive to the adolescent and smoking population and trained to monitor any potential adverse effects. Heart rate, blood pressure, and pulse oximetry will be assessed at baseline and every in-person visit for safety. If they experience any side effects or concerns during the study, we ask them to let us know. Participants will be told that they are able to stop the study at any point. If they feel any discomfort or need to stop for any reason, they can let the research team know. In the event of a serious adverse event, the PI ([name]), will consult with Yale Tobacco Center for Regulatory Science (TCORS; the funder of

this pilot) co-Is, [name] [name] and [name], along with center chemosensory expert [name] to determine if blind needs to be broken. Given all study participants are administered all e-liquids, the study will be paused during this period.

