acute responses to the e-cig on a 0 to 100 mm scale, from “not at all” to “extremely.” Following each 10-puff bout, we will assess E-cig Liking/Wanting (average of “I feel good e-cig effects”, “I want more of that e-cig I received”, “I feel the e-cig strength” and “I like the e-cig effect”). At baseline and following each fixed-dose bout, we will also assess Stimulant effects (average of “I feel energized” and “I feel high”), and Nicotine Withdrawal (average of “I feel sleepy”, “I feel angry”, “I feel irritable”, “I am having difficulty concentrating”, “I feel restless” and “I feel hungry”). **E-cig Effects will be used to assess change in overall appeal (primary outcome).**

4. Multiple Choice Questionnaire to assess e-cig value (Adapted from Multiple Choice Procedure (MCP))^{25,26}: At the end of each 2-puff puff bout, participants will be asked to make discrete hypothetical choices between 10-puffs of the e-cig they had just used or a series of 44 monetary values (\$0.25-\$15.06). The minimum monetary value at which money is chosen over the e-cig puffs is a contingency-based estimate of e-cig value. At the end of each lab session, participants will be given a choice between another 10 e-cig puffs or one of the monetary amounts they picked in the MCPs completed earlier. **MCP will be used to assess change in overall appeal (primary outcome).**

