completion of baseline assessments, at Lab 1, participants will be familiarized with the sensory and hedonic scales and trained in how to puff the e-cigarette (using non-nicotine and non-flavored e-liquid). Participants will then begin testing procedures for their assigned Flavor 1, which will be administered under double-blinded randomized conditions (see above). For each flavor, participants will take two puffs of the flavor when diluted by four levels of water concentration. Participants will be instructed to take two 3-second puffs with a 30 second inter puff interval. Each two-puff bout will be separated by 10-minutes. These procedures are adapted from our recent work (HIC #2000023077), with the number of puffs is reduced as we are not examining the effects of nicotine and only sensory effects of flavor. Per our current practice we will record timed instructions for each puff bout and participants will be trained to follow these directions. Following each puff exposure participants will complete the General Labeled Magnitude Scale (gLMS) for measures of overall intensity, irritation, coolness and sweetness, the Labeled Hedonic Scale (LHS) for measures of liking, the E-Cig Effects Questionnaire for measures of e-cigarette drug effects, and the Multiple-Choice Questionnaire to assess e-cigarette value. Participants will complete the above procedures for two flavors and four water concentrations for each flavor during each lab session. For each flavor, water concentration order will not be randomized and will be presented from hypothesize least irritating (20% water concentration) to hypothesized least irritation (e-liquid as commercially available with no water dilution) to a) maintain consistency of presentation of water concentration across flavors and b) to avoid potential irritation effects from hypothesized more irritating products to less irritating products. Following at least 24 hours, participants will repeat procedures with the remaining two flavors. Each lab session will last approximately two hours.

Debrief

At the end of Lab 2, participants will be thanked for their participation and ask to evaluate the four flavors they sampled (i.e. guess what flavors they tried, what nicotine concentration they e-liquids were) and will be given information from the CDC on e-cigarette cessation.

Table 1. List of Study Assessments

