	Pre-screening (Pre-consent)	Intake	Lab 1 Baseline Assessments	Lab 1Assessments Following each E-Liquid Administration	Lab 2 Baseline Assessments	Lab 2 Assessments Following each E-Liquid Administration
Contact Info & Eligibility Review	X					
Informed Consent		X				
Identifying Information		X				
Demographics		X				
30-day Timeline Follow-back		X				
Tobacco & E-Cigarette Use History		X				
Medical History		X				
E-Cigarette Dependence Scale		X				
Cotinine & Urine Drug Screen		X				
Asthma Control Test		X	X		X	
PROMIS Fatigue		X	X		X	
PROMIS Dyspnea		X	X		X	
FACIT Cough Question		X	X		X	

EVALI Health Assessment		X	X		X	
General Labeled Magnitude Scale (gLMS)				X		X
Labeled Hedonic Scale (LHS)				X		X
E-Cigarette Drug Effects				X		X
Multiple Choice Questionnaire				X		X
Heart Rate, Blood Pressure, Pulse Oximetry		X	X		X	
Pregnancy Test		X	X		X	
Debrief						X

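### Timing of the E-cig Effects ratings conflicts between sections: Liking/Wanting is tied to a 10-puff bout that no rated exposure uses, and the required session baseline has no mark in Table 1

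*Combined protocol and SAP*

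**What the plan says.** Section 6.2.1, item 3, gives two timing rules for the E-cig Effects questionnaire (the adapted DEQ). For one score it says "Following each 10-puff bout, we will assess E-cig Liking/Wanting". For the other two, Stimulant effects and Nicotine Withdrawal, the sentence begins "At baseline and following each fixed-dose bout, we will also assess Stimulant effects". The term for the bout in that second rule is not defined anywhere. The item closes by giving the whole questionnaire primary status: "E-cig Effects will be used to assess change in overall appeal (primary outcome". The Synopsis also names it in the second primary outcome: "Change in appeal at each water level as measured by the Labeled Hedonic Scale (LHS), Drug Effects Questionnaire (DEQ".

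The exposure is described differently elsewhere. The E-liquid Administration paragraph (under 6.1.2 and 6.1.3) has participants "take two directed puffs of each e-liquid at each water concentration". Section 6.3, Lab Visits, says "Participants will be instructed to take two 3-second puffs with a 30 second inter puff interval". It then lists the ratings in a sentence that opens "Following each puff exposure participants will complete the General Labeled Magnitude Scale (gLMS" and goes on to include the E-Cig Effects Questionnaire. For what is completed on arrival at a session, 6.3 refers the reader to the visit schedule. In that schedule (Table 1), the row "E-Cigarette Drug Effects" is marked only in the Lab 1 and Lab 2 columns for assessments after each administration. Neither baseline column is marked.

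**The concern.** A measure labelled primary should have one unambiguous rating time, and here the section that defines the measure disagrees with the procedure and the schedule on two counts. First, staff reading 6.2.1 alone would look for a 10-puff bout to attach Liking/Wanting to, and no rated bout has ten puffs. Second, a data-capture form built from Table 1 would have no pre-exposure Stimulant or Withdrawal rating, although 6.2.1 asks for one. A pre-exposure rating that is not taken on the day cannot be reconstructed.

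The second conflict matters more for analysis. Participants abstain for only two hours before a session, checked by self-report, so their starting withdrawal and stimulation may differ from one session to the next. Each session covers two of the four flavors, so many flavor comparisons are also comparisons between sessions. The session baseline is the only planned measure of that difference in starting state on these two scores.

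**Working it through.** 1. **The plan's own exposure figure.** Inputs: 4 flavors and 4 water levels (6.1.4), 2 puffs per bout (6.3), 2 sessions (5.1). Bouts = 4 x 4 = 16. Puffs = 16 x 2 = 32, and 32 / 2 = 16 per session. Section 3.2.1 states 32 and 16, so the figures reproduce. With 10-puff rated bouts the total would be 16 x 10 = 160, or 80 per session, five times the stated exposure.

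2. **Where ten puffs do occur.** They appear only in the Multiple Choice item of 6.2.1: as a hypothetical option after each 2-puff bout, and as an optional end-of-session choice against money. No E-cig Effects rating is scheduled after that choice.

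3. **Reading of Table 1.** The E-Cigarette Drug Effects row has marks in 2 columns, both post-administration, and 0 of 2 baseline columns. This does not look like a text-extraction fault. The gLMS, LHS and Multiple Choice rows show the same pattern, while the PROMIS, FACIT and EVALI rows carry both baseline marks.

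4. **Records at risk.** 30 participants x 2 sessions = 60 session baselines. Each holds 2 Stimulant items and 6 Withdrawal items, so 8 items.

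5. **Effect on the water contrasts.** All four water levels of a flavor are tested in one session. Let B be the session baseline and b its slope. The adjusted contrast is (Y at 20% - bB) - (Y unaltered - bB) = Y at 20% - Y unaltered, so B cancels. Nor does B remove drift under the fixed order. Suppose ratings fall by 2 points per bout with no water effect (an assumed value). Within a flavor, 20% water is bout 1 and unaltered is bout 4, so the false contrast is 3 x 2 = 6 points, with or without B.

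6. **Effect on the flavor contrasts.** Four flavors make 6 pairs. Two flavors per session puts 2 pairs within a session and leaves 6 - 2 = 4 across sessions. Of the 3 aldehyde pairs, the session without grape holds 1, so 2 cross sessions. For a cross-session pair, let r be the within-person correlation between the difference in session baselines and the difference in ratings. Adjustment multiplies the standard error by the square root of (1 - r²), ignoring the small cost of estimating the slope. The documents give no value for r, so these are assumptions:
   - r = 0.24: square root of 0.942 = 0.97, a cut of about 3%.
   - r = 0.50: square root of 0.750 = 0.87, a cut of about 13%.
   - r = 0.77: square root of 0.407 = 0.64, a cut of about 36%.

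   The gain on a flavor contrast over the whole sample is smaller, because some participants have that pair within one session.

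**The case against.** The strongest reply is that this is an editing slip with little consequence. Section 6.3 and Table 1 both place the questionnaire after each administration, and the bout size is two puffs wherever exposure is described, so the intended time for Liking/Wanting is clear. Table 1 is also not exhaustive: spirometry at session arrival, and saliva and breath carbon monoxide at intake, are required in the text but have no row. Since 6.2.1 still instructs the baseline ratings, staff may collect them anyway. Finally, no planned analysis uses them. In the primary objective, baseline means the starting water concentration, and 6.4.1 and 6.5.1 include no pre-exposure covariate.

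Most of this stands, and it rules out three stronger readings that a reader might infer.

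- **That Liking/Wanting will be lost for all 30 x 16 = 480 bout ratings.** This would require staff to ignore both 6.3 and Table 1. It is the bound under a literal reading of one sentence, not an expected loss.
- **That without the baseline, relief from abstinence cannot be separated from the water effect, and that adding the baseline cures this.** Step 5 of the working shows that the baseline cancels. A drift that is linear over the session can be estimated without it, because two flavor blocks put 20% water at bouts 1 and 5 and unaltered liquid at bouts 4 and 8. Confounding of water level with order inside a block is a separate design matter.
- **That all three scores are equally primary and equally affected.** Section 6.2.1 labels the whole questionnaire primary, but 5.2 describes the DEQ as measuring liking and stimulation and does not mention withdrawal. The baseline rule does not apply to Liking/Wanting.

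The reply does not remove the contradictions. The protocol asks for a baseline that its schedule omits, and the procedures text lists the questionnaire only after puffs.

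**Conclusion.** The point holds as an internal inconsistency with a modest analytic cost. Item 3 of 6.2.1 contradicts the exposure and procedure sections on when Liking/Wanting is rated. It also contradicts Table 1 on whether Stimulant and Withdrawal are rated before exposure. If Table 1 governs, up to 60 session baselines go uncollected. The planned water contrasts are unaffected. The loss is precision in the flavor contrasts that cross sessions, four of six pairs per participant and two of three among the aldehyde flavors, which serve the secondary objective. The 3% to 36% reduction in standard error rests on assumed correlations of 0.24 to 0.77. If starting state hardly varies between sessions, the gain is close to nil. The change is worth making because it is cheap and a missed baseline cannot be recovered.

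**What to change.** - Reconcile item 3 of 6.2.1 with 6.3 and Table 1, so that Liking/Wanting is rated after each 2-puff bout together with gLMS, LHS and the Multiple Choice Questionnaire. Replace the undefined bout term in the Stimulant and Withdrawal sentence with the same wording. This concerns when the questionnaire is given and implies no change to exposure.
- Mark E-Cigarette Drug Effects in the Lab 1 and Lab 2 baseline columns of Table 1, with a note that only the Stimulant and Withdrawal items apply there.
- In 6.4.1 and 6.5.2, state that the session baseline is a covariate for Stimulant and Withdrawal in the flavor models. Entering it as the deviation from the participant's mean over the two sessions targets the cross-session difference directly. State also that it is not a remedy for the fixed water order.
- The protocol reports that enrollment has begun. For any sessions already run, record whether the baseline was taken.

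The cost is a few words, two marks in Table 1, about one minute of questionnaire time per session and one added model term. If the sponsor does not want the baseline, deleting it from item 3 would also resolve the contradiction, at the price of the precision described.

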6.2.2 Safety and Pregnancy-related policy

Women who report pregnancy, trying to become or breastfeeding will be excluded from the study. All participants will be informed if pregnancy status changes to inform staff. Participants will be given a urine pregnancy test at every visit.

6.2.3 Adverse Events Definition and Reporting

During screening, participants will undergo a review of their medical history and a brief physical (blood pressure, spirometry, heart rate, pulse oximetry, urine drug and pregnancy test) to assess health. Participants with chronic and untreated acute pulmonary conditions, current, untreated psychiatric conditions, or any other condition that could interfere with study participation/meets exclusion criteria will not be enrolled. Special attention will be placed on serious mental health issues not being treated and those at risk will be encouraged to seek mental health treatment. Participants will be terminated from participation if the investigator feels that their health or well-being may be threatened by continuation in the study. All participants will receive educational material of tobacco product use at the end of their study participation. We will measure health status throughout the study by using self-report questionnaires to assess fatigue, dyspnea, asthma and overall health with a checklist of symptoms related to the reported vaping illnesses. These assessments will be administered at every in-person visit. We will also assess heart rate, blood pressure, and pulse oximetry at baseline and every in-person visit.

This protocol presents a minor increase over minimal risk to the subjects and adverse events are not anticipated. In the unlikely event that such events occur, serious and unanticipated and related adverse events will be reported in writing within 48 hours to the Yale IRB and NIDA. The initial SAE report will be followed by submission of a completed SAE report to both institutions. In the event that a participant either withdraws from the study or the investigator decides to discontinue a participant due to an SAE, the participant will be monitored by the investigator via ongoing status assessment until 1) a resolution is reached

i.e., the problem requiring hospitalization has resolved or stabilized with no further changes expected 2) the SAE is determined to be clearly unrelated to the study intervention, or 3) the SAE results in death. Outcome of SAEs will be periodically reported to NIDA. A summary of the SAEs that occurred during the previous year will be included in the annual progress report to NIDA.

The principal investigator, [name], will be responsible for evaluating the adverse events and study data at regular intervals and determine whether the adverse event affects the Risk/Benefit ratio of the study and whether modifications to the protocol (at Risks to Subjects) or consent form (at Risks and Inconveniences) are required. During the review process, the PI will evaluate whether the study should continue unchanged, require modification/amendment, continue or close to enrollment. If necessary, PI will consult with study physician. Either the PI or the IRB or the DSMB have the authority to stop or suspend the study or require modifications. The review of all adverse events by the PIs will determine the attribution and grade of severity of the adverse event by using the following scales:

Attribution of Risk Categories:

Definite: There is clear evidence to suggest a causal relationship, and other possible contributing factors can be ruled out. The clinical event, including an abnormal laboratory test result, occurs in a plausible time relationship to study intervention administration and cannot be explained by concurrent disease or other drugs or chemicals. The response to withdrawal of the study intervention (dechallenge) should be clinically plausible. The event must be pharmacologically or phenomenologically definitive, with use of a satisfactory rechallenge procedure if necessary.

Probable: There is evidence to suggest a causal relationship, and the influence of other factors is unlikely. The clinical event, including an abnormal laboratory test result, occurs within a reasonable time after administration of the study intervention, is unlikely to be attributed to concurrent disease or other drugs or chemicals, and follows a clinically reasonable response on withdrawal (dechallenge). Rechallenge information is not required to fulfill this definition.

Possible/Potential: There is some evidence to suggest a causal relationship (e.g., the event occurred within a reasonable time after administration of the trial medication). However, other factors may have contributed to the event (e.g., the participant's clinical condition, other concomitant events). Although an AE may rate only as "possibly related" soon after discovery, it can be flagged as requiring more information and later be upgraded to "probably related" or "definitely related", as appropriate.

Unlikely: A clinical event, including an abnormal laboratory test result, whose temporal relationship to study intervention administration makes a causal relationship improbable (e.g., the event did not occur within a reasonable time after administration of the study intervention) and in which other drugs or chemicals or underlying

disease provides plausible explanations (e.g., the participant's clinical condition, other concomitant treatments).

Unrelated: The AE is completely independent of study intervention administration, and/or evidence exists that the event is definitely related to another etiology. There must be an alternative, definitive etiology documented by the clinician.

Grades of Risk:

- 0: No adverse event or within normal limits
- 1: Mild adverse event; Events require minimal or no treatment and do not interfere with the participant's daily activities.
- 2: Moderate adverse event; Events result in a low level of inconvenience or concern with the therapeutic measures. Moderate events may cause some interference with functioning.
- 3: Severe adverse event resulting in hospitalization or prolongation of existing hospitalization, a persistent or significant disability/incapacity, or a congenital anomaly/birth defect; Events interrupt a participant's usual daily activity and may require systemic drug therapy or other treatment. Severe events are usually potentially life-threatening or incapacitating. Of note, the term "severe" does not necessarily equate to "serious".]
- 4: Life-threatening or disabling adverse event
- 5: Fatal adverse event

Expectedness:

The Principal Investigator will be responsible for determining whether an AE is expected or unexpected. An AE will be considered unexpected if the nature, severity, or frequency of the event is not consistent with the risk information previously described for the study intervention.

